Appendix 2:	Informed Consent Document	Error! Bookmark not defined.	
Appendix 3:	Informed Consent Document	Error! Bookmark not defined.	
Appendix 4:	Questionnaire for the evaluation of	Mood DisordersError! Bookmark not defined.	
Appendix 5:	Serious Adverse Event Report Form	31	

List of abbreviations

BMI Body mass index
BP Blood pressure
CRF Case record form

CBC Complete blood count
CI Confidence interval

FDA Food and Drug Administration
FSH Follicle stimulating hormone

GCP Good Clinical Practice

ICH International Conference on Harmonization
IND Investigational New Drug Application

IRB Institutional Review Board

LC/MS Liquid chromatography/mass spectroscopy

LH Luteinizing hormone

Medical Dictionary for Regulatory Activities

NICHD National Institute of Child Health and Human

Development

OAT Oligoasthenoteratozoospermia

SAE Serious adverse event

T Testosterone

Synopsis

Study Title	A randomized, placebo-controlled trial of 13- cis retinoic acid for the treatment of men with oligoasthenoteratozoospermia
Study	II
Phase	
Sponsor	National Institute of Child Health and Human Development
Study Drug	13-cis retinoic acid
Objective	Primary Objective: To determine the effect of 13-cis retinoic acid administration on total motile sperm count in men with oligoasthenoteratozoospermia Approach: Sixty men with infertility due to oligoasthenoteratozoospermia (total, motile sperm count of <10 million), but not known genetic abnormalities, will be enrolled in a prospective six-month, randomized, double-blinded, placebo-controlled 3-arm pilot trial of daily oral therapy with placebo, 20 or 40 mg daily of 13-cis retinoic acid. The impact of treatment on spermatogenesis will be determined by monthly semen analysis. Secondary Objectives: • To determine the chance of pregnancy during treatment with 13-cis retinoic acid • To determine the concentration of 13-cis retinoic acid in the seminal plasma of treated men • To determine the side effects associated with treatment with 13-cis retinoic acid
Principal	[name] MD, MPH
Investigator	
Rationale	Men with infertility and normal gonadotropins have few options for treatment. Recent research has demonstrated the lower intratesticular concentrations of 13-cis retinoic acid are associated with abnormal sperm parameters. Older studies of 13-cis retinoic acid administration to normal men demonstrated increases in sperm concentrations, but the effect of 13-cis retinoic acid on sperm concentrations in men with infertility has never been studied. If 13-cis retinoic acid increased sperm concentrations in infertile men, it could help infertile men father pregnancies without the need for IVF and/or ICSI.

Study	This is a prospective, randomized, double-blinded, trial to
Design	evaluate 13-cis retinoic acid for the treatment of
	oligoasthenoteratozoospermia
	We will conduct a prospective, three-arm, randomized, double-blinded, placebo-controlled interventional trial to determine the impact of therapy with 13-cis retinoic acid on sperm indices in infertile men. Sixty (n=20/group) infertile men with abnormal sperm analyses will be enrolled in a 24-week study of 20mg or 40 mg of 13-cis retinoic acid or matching placebo daily. The subjects will be closely followed for side effects related to treatment. The impact of treatment on indices of spermatogenesis will be determined by monthly seminal fluid analyses.
	All aspects of this study will be performed in compliance with Good Clinical Practice (GCP) regulations, ICH guidelines, the Declaration of Helsinki, and under an FDA Investigational New Drug (IND) application.
Number of	Sixty men.
Subjects	
Duration of	Enrolment should be completed in about 12 months,
Trial	resulting in total study duration of about 24 months including screening, treatment phase, end of study visit procedures, close out and data analysis.
Duration of	The active treatment phase will be 24 weeks
Treatment	
Dosage and Regimen	13-cis retinoic acid at 20 or 40 mg daily or matching placebo
Inclusion	Subjects will be infertile men (no pregnancy with partner with
Criteria	normal cycles and normal hysterosalpingogram despite >1 year of unprotected intercourse) and abnormal sperm analyses with a total, motile sperm count of less than 10 million sperm as assessed by semen analysis on two occasions separated by one week
Exclusion	Exclusion criteria include: known genetic infertility (e.g.
Criteria	Klinefelter syndrome or Y-chromosome microdeletions), hypogonadotropic hypogonadism (that might respond to gonadotropin injections), the use of anabolic steroids, illicit drugs, or the consumption of more than 4 alcoholic beverages daily, severe mental health problems, or current therapy with retinoic acid (e.g. Accutane) or vitamin A.

Efficacy	In this study, count of total, motile sperm after 24 weeks of
Parameters	treatment.
Safety	CBC, clinical chemistry panel (glucose, liver and renal
Parameters	function tests including urea, creatinine, albumin, alanine aminotransferase, aspartate aminotransferase, alkaline phosphatase, bilirubin), full lipid panel including Total cholesterol, HDL, LDL, triglycerides at screening and at the end of treatment. Additional measures will be conducted if any abnormal values are found until the end of study visit. • Adverse event and concomitant medications throughout the study. Other safety parameters include vital signs; and changes in pre- and post-treatment physical examination results and score on the PHQ9 depression questionnaire.
Evaluations	The following determinations will be made in all subjects: • Serum samples will be collected for the measurement of concentrations of vitamin A, all-trans and 13-cis retinoic acid, testosterone, FSH and LH will be collected before the beginning of the treatment, and monthly during treatment.
Other Assessments	Demographic characteristics, including age and race, will be collected
Statistical	The primary endpoint is the effect of treatment on the count
	of total, motile sperm between treatment groups after 24
Analysis	weeks. This analysis will be conducted using a Kruskal-Wallis ANOVA is the primary endpoint.

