12.4 Visits in treatment period

Seven visits will occur in the treatment period: week 0, week 4, week 8, week 12, week 16, week 20 and week 24. All visits are \pm 4 days.

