12.4.1 Visit 1 (week 0)

This is the day 1 of treatment. The following will be done at this visit:

- Vital signs (pulse, blood pressure, respiratory rate) and weight will be taken and recorded.
- Subjects will be questioned regarding concomitant medications and adverse events. If the subject is taking a medication that is listed as disallowed the subject should not be enrolled in the study.
- The subject will complete the PHQ9 questionnaire (see appendix xx)
- A blood samples will be drawn, and the time of day of the blood draw will be noted in the CRF.
- A semen sample will be obtained for the measurement of sperm count, concentration, motility and morphology.
- Subjects will be given enough supply of study medication for 30 days (plus a supply for 2 additional days in the event of scheduling issues) as per their assigned group.
- A study medication log will be dispensed to record the date and time of administration of the study medication. Subjects will be instructed to take the medication in the morning, except on the day of the visit. Subjects will be scheduled to return to the clinic after 28 ± 4 days.

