12.4.2 Visits 2-7

These visits are for weeks 4,8,16, 20 and 24. The following procedures will be done at each of these visits:

- Vital signs (pulse, blood pressure, respiratory rate) and weight will be taken and recorded.
- The subject will complete the PHQ9 questionnaire
- Complete physical exam including testicular examination and volume measurement will be performed.
- Subjects will be questioned regarding concomitant medications and adverse events.
- Any unused study medication will be collected at this visit.
- Study medication log will be reviewed to check the date and time of drug administration. These logs will be collected at this visit.

 A blood sample will be drawn. The time of day of the blood draws will be recorded in the source.

- A semen sample will be obtained for the measurement of sperm count, concentration, motility and morphology
- Fasting blood samples will be obtained for the following measurements: CBC, clinical chemistry including glucose, liver and renal function tests (urea, creatinine, albumin, alanine aminotransferase, aspartate aminotransferase, gamma glutamine transferase, alkaline phosphatase, bilirubin, and albumin), full lipid panel including total cholesterol, HDL and LDL, triglycerides, hematology (hematocrit, hemoglobin), and testosterone, FSH and LH. In addition, two serum samples will be frozen for the future analysis of serum retinoid levels.
- Subjects will be given the next month's supply of medication.
- Subjects will be scheduled to return to the clinic after additional 4 weeks visit.

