12.4.3 Visit 8 and 9 (Follow-up Visits)

The following will be done at this visit:

- Vital signs (pulse, blood pressure and respiratory rate) will be taken and recorded.
- The subject will complete the behaviour questionnaire
- Subjects will be questioned regarding concomitant medications and adverse events.
- A blood sample will be drawn for the measurement of serum FSH, LH, T, and retinoids.
- A semen sample will be obtained for the measurement of sperm count, concentration, motility and morphology

13. Study Withdrawals

Subjects withdrawing from the study can be replaced only if the withdrawal occurs before the start of the treatment. Subjects who have had medication will not be replaced, regardless of the reason for discontinuation. All efforts should be made to contact any subject who decides to discontinue study participation for the end of study safety procedures (Visit 9). The necessary clinical and laboratory examinations planned at the last visit should be performed at the end of the study whenever it occurs. The reasons for discontinuation will be documented.

Post-Admission Withdrawal Criteria

Subjects may be discontinued prematurely for any of the following reasons:

• Emergence of a severe condition(s) such that, in the judgment of the investigator, continuation in the trial would negatively impact the health of the subject.

- Personal reasons (e.g. withdrawn consent).
- Subject lost to follow-up

All subjects in a treatment arm may be discontinued prematurely if greater than 25% of the subjects in an arm are discontinued for the emergence of the same severe condition that requires individual subjects to be discontinued.

14. Statistical Considerations

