14.3 Safety

Laboratory data, physical examination results, vital signs and chemistry levels will be assessed and compared for each subject from screening to end of study. All adverse events will be recorded and coded using the body system coding of MedDRA.

The incidence of adverse events will be examined by dose and where appropriate for trend by subject, clinic and time, using descriptive statistics. Clinical chemistries and allied data will be examined for change over time.

15. Adverse Events

Adverse Events (AE) should be carefully monitored and an AE form is included in the CRF. Serious adverse events (SAE) as defined below will have to be reported on the SAE form included as an appendix.

All adverse experiences must be recorded in the study event record of the subject's CRF, and must include the following information (when applicable):

- Specific condition or event
- Indication of whether the condition was pre-existing or not and if yes, whether it has worsened in severity (including an increase in frequency)
- Date of occurrence
- Date of resolution
- Relationship to study medication as evaluated by the investigator (causality assessment). The investigator must enter their opinion of causality on the AE forms.
- Action taken (study medication continued or not) and outcome
- Seriousness according to the approved regulatory classification {i.e. any event that is fatal, life-threatening, disabling, incapacitating, results in or prolongs hospitalization, or is a medically significant event, e.g. an intervention to prevent one of the above outcomes, or any other serious criteria (cancer, congenital anomaly, overdose, other significant) is considered serious}.

When any serious adverse drug experience, regardless of causality, is encountered during this clinical trial at an investigator's site, the investigator must notify the Study Monitor by facsimile using the form provided as an appendix. This report must be submitted within 2 calendar days from the time the investigator's staff is notified of the event.

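### PHQ-9 is scored at six on-treatment visits, but its only stated use is a pre- to post-treatment change, which draws on at most one of the six scores

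*Combined protocol and SAP*

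**What the plan says.** **Collection.** Section 12.4 sets the calendar: "Seven visits will occur in the treatment period: week 0, week 4, week 8, week 12, week 16, week 20 and week 24". Section 12.4.1 has PHQ-9 completed at week 0, which is Day 1. Section 12.4.2, for Visits 2-7, repeats the instruction: "The subject will complete the PHQ9 questionnaire". The Schedule of Events (Appendix 1) marks PHQ-9 at both screening visits, Day 1, all treatment visits and follow-up. For the two follow-up visits, section 12.4.3 says only "The subject will complete the behaviour questionnaire".

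**Use.** The one statement on what is done with the score is in the Synopsis, Safety Parameters: "changes in pre- and post-treatment physical examination results and score on the PHQ9 depression questionnaire". Section 14.3 (Safety) opens with "Laboratory data, physical examination results, vital signs and chemistry levels will be assessed" and compares these within each subject from screening to the end of the study. It then covers adverse events by dose and closes with "Clinical chemistries and allied data will be examined for change over time". PHQ-9 is not named in that section.

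**The concern.** Side effects and tolerability are a secondary objective (section 2.2), and PHQ-9 is the only mood scale the protocol identifies. The schedule follows mood every four weeks, while the stated summary compares two points. If that summary is all that is reported, the scores from weeks 4 to 20 play no part in it. A rise in depressive symptoms early or midway through treatment that has settled by week 24 would then show in the safety results only if it was also recorded as an adverse event. The plan also does not say which score is the pre-treatment one (screening or Day 1) or which is the post-treatment one, and it mentions no comparison of PHQ-9 between arms.

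**Working it through.** The plan gives no figure to reproduce. The check is a count of scores collected against scores used, followed by a reading of section 14.3.

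**1. On-treatment scores per man.** Section 12.4 lists seven visits, one of which is week 0, so 7 - 1 = 6 are on treatment. Section 12.4.2 lists only five weeks (week 12 is missing), but its heading covers Visits 2 to 7, which is six visits, and Appendix 1 lists weeks 4, 8, 12, 16, 20 and 24. Six is the right count.

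**2. Planned total.** Section 7 gives 60 men, 20 per arm. With full attendance, 60 x 6 = 360 on-treatment scores.

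**3. Scores used by the stated summary.** This depends on what post-treatment means.

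| Reading of the Synopsis phrase | On-treatment scores used | Not used |
|---|---|---|
| Week 24 | 60 of 360 (60/360 = 17%) | 300 (weeks 4-20: 60 x 5) |
| Week 28 or 36 follow-up | 0 of 360 | 360 |
| A list of parameters only | no summary stated | not applicable |

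Week 24 is the plainest reading, because the same Synopsis cell times the laboratory work as "full lipid panel including Total cholesterol, HDL, LDL, triglycerides at screening and at the end of treatment". The follow-up reading is possible, because section 6 describes the visits 4 and 12 weeks after treatment as post-treatment. At most one of the six scores is used on either reading.

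**4. Whether section 14.3 fills the gap.** Its first sentence lists four kinds of data, and PHQ-9 is not one of them. Its last sentence, on change over time, attaches the undefined term for allied data to clinical chemistries. Even if that term is stretched to include a questionnaire, it gives no time points, no statistic and no comparison by arm.

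**5. What the week-24 form can show.** Appendix 4 asks about the preceding two weeks, so the week-24 form covers weeks 22 to 24 (24 - 2 = 22).

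- A rise that ended before week 22 is outside the form.
- A rise that ended between weeks 22 and 24 may or may not lift the score, because the items grade frequency.
- A rise still present at week 24 is captured.

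**6. What cannot be computed.** The proportion of mood changes missed depends on when they start and how long they last. The documents give neither. If every rise lasts to week 24, nothing is lost; the shorter and earlier the rises, the more is lost. The count in step 3 is the only size the documents support.

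**The case against.** The strongest reply is that the Synopsis cell is shorthand. It times the laboratory tests at screening and end of treatment only, yet section 12.4.2 and Appendix 1 draw them at every treatment visit and section 14.3 examines chemistries over time. A cell that does not limit the laboratory tests to two points is weak evidence that PHQ-9 is limited to two. This stands in part: no sentence says that the week 4-20 scores will be set aside, and a reader who inferred a decision to discard them would go beyond the text. But the laboratory tests have the change-over-time sentence in section 14.3 to supply what the Synopsis leaves out, and PHQ-9 has no such sentence. If the Synopsis phrase is only a list, then no PHQ-9 summary is stated at all, and the remedy is the same.

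Second, adverse events are asked about at every visit and examined by dose and, where appropriate, for trend over time. This stands: a mood problem reported that way is not lost, and the gap is confined to rises that are both unreported and over before week 24.

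Third, other repeated measures, such as vital signs, are also summarised briefly, which is ordinary in a 60-man pilot. That is fair and limits the severity. Vital signs are at least named in section 14.3.

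A reader might infer from the 17% that five-sixths of mood harm would be missed. The documents do not support that: 17% is a share of forms, not of episodes, and a persistent effect is fully visible at week 24.

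**Conclusion.** The point holds as a cheap improvement to the safety summary. As written, the plan's one stated use of PHQ-9 draws on at most 60 of 360 planned on-treatment scores, and section 14.3 does not add to it. The consequence is limited to a rise that resolves before week 24 and is not reported as an adverse event. The count assumes full attendance and a week-24 reading of post-treatment; on the follow-up reading no on-treatment score is used. The amount of harm missed cannot be determined from the documents.

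The primary endpoint, randomization and data collection are unaffected, and all scores are still collected. No claim is made about men who stop early, because section 13 asks for the last-visit examinations whenever the man's study ends, which leaves the timing of his final form open.

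**What to change.** In the Synopsis and section 14.3, replace the pre/post PHQ-9 change with a descriptive summary by arm, shown beside placebo: change in PHQ-9 from Day 1 at each of weeks 4, 8, 12, 16, 20 and 24, using all values up to stopping. Show weeks 28 and 36 separately, and name PHQ-9 in section 12.4.3 so that those forms are clearly the same scale. This change alone closes the gap.

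Two additions are optional:

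- The number of men per arm with a new non-zero answer to item 9 (self-harm) on treatment, meaning zero on Day 1.
- The worst on-treatment change from Day 1, read only against placebo, because the highest of six scores exceeds Day 1 by chance in every arm. With no drug effect, simulation gives a mean excess of about 0.7 to 0.9 SD for correlations between visits of 0.7 to 0.5. It is also imprecise: with spreads of 0.653 and 0.840 SD, the 95% half-width for 20 against 20 men is 2.02 x 0.653 x sqrt(2/20) = 0.42 SD to 2.02 x 0.840 x sqrt(2/20) = 0.54 SD. The correlations and normal scores are assumptions, and PHQ-9 is bounded at zero, so these figures are rough. Men who stop early have fewer scores, so their worst value is less inflated.

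The cost is a few lines of text and one or two extra descriptive tables. No new data, visits or tests are needed.

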1.0 Introduction and Background

Infertility affects 10-15% of all couples, with 1.5 million couples seeking medical assistance for infertility yearly (1). Infertility attributable to the male partner accounts for 30-40% of all cases of infertility. The most common form of male infertility involves some type of impairment in spermatogenesis (2). Unfortunately, over 80% of men with infertility from impaired spermatogenesis do not have a medically treatable cause, such as a gonadotropin deficiency (3). In men with idiopathic infertility, surgical sperm extraction from the testis coupled with *in vitro* fertilization or intra-cytoplasmic sperm injection offers some hope of fertility; however, these procedures are invasive, expensive, unsuccessful in 30-40% of cases, and don't address the underlying cause of infertility (4). Therefore, new approaches to the treatment of male infertility are sorely needed.

The essential role of vitamin A (retinol) in spermatogenesis has been long appreciated. Vitamin A deficient male mice are sterile due to impaired spermatogenesis and supplementation of deficient mice with vitamin A restores fertility (5, 6). Vitamin A is required for spermatogenesis as it is converted to retinoic acid in the seminiferous tubules via the activity of testes-specific retinol and retinal dehydrogenases. Retinoic acid is known to mediate most of the effects of vitamin A in tissues. In the testes, two retinoic acid receptors, α and γ , are present in both Sertoli cells and developing germ cells (7-10), and targeted deletion of these receptors in mice results in male infertility (11-13). From this work, it is clear that retinoic acid plays several essential roles in spermatogenesis, including necessary functions in spermatogonial differentiation, spermatid adhesion to Sertoli cells and spermiation (14). Given the crucial role of retinoic acid in spermatogenesis, it seems quite possible that some men with "idiopathic" infertility have intratesticular concentrations of retinoic acid below those necessary to initiate and/or maintain optimal spermatogenesis, but whether relative deficiencies of intratesticular retinoic acid contribute to male infertility in humans is unknown. In theory, poor dietary intake of vitamin A could lead to infertility; however, a nutritional cause of infertility seems improbable in the US. More likely, low intratesticular concentrations of retinoic acid could occur in infertile men either due to impaired retinoic acid biosynthesis from vitamin A or increased metabolism of retinoic acid to inactive metabolites within the testes.

Despite the known importance of retinoic acid for spermatogenesis in animals, there has been relatively little work examining the role of retinoic acid on spermatogenesis in humans. In this proposal, we will perform a clinical trial of retinoic acid administration to infertility patients to determine whether retinoic acid therapy improves sperm quality in infertile men. Intriguingly, there is a suggestion that the administration of retinoic acid to men may improve sperm production. During the development of 13-cis retinoic acid (Accutane) for acne, three human studies examining the effect of oral administration of 13-cis-retinoic acid on sperm production in men were performed to determine if 13-cis retinoic acid was harmful to male fertility. Interestingly, men in these studies had increased sperm concentrations during treatment (see below), suggesting that 13-cis retinoic acid administration enhanced spermatogenesis in these normal men with acne (15-17).

If the administration of retinoic acid were shown to improve spermatogenesis in some infertile men, it would have tremendous significance for our current approach to the treatment of male infertility. Because of its widespread use in humans for over 25 years, 13-cis retinoic acid is widely available in a generic formulation and could be quickly incorporated into male infertility treatment algorithms. Ideally, retinoic acid therapy would increase an infertile man's chances of successfully fathering a pregnancy without the need for assisted reproductive technologies such as intra-cytoplasmic sperm injection and/or surgical methods of sperm extraction that are invasive for both the man and the woman, expensive and fail in many of cases.

Our group has completed the first ever study in humans to examine intratesticular retinoic acid concentrations. With IRB approval, we enrolled 24 men having scrotal surgery in an observational study to examine the association between intratesticular

retinoids and spermatogenesis. Interestingly, we observed that intratesticular 13-*cis* retinoic acid is significantly lower in men with sub-normal sperm quality as compared to men with normal sperm quality as defined by the WHO criteria (18) (Figure 1).

[figure not shown]

Figure 1. Intratesticular 13-*cis* retinoic acid in 24 men expressed as median and interquartile ranges. 13-*cis*-retinoic acid is significantly lower in men with sub-normal sperm quality as compared to men with normal sperm analyses (p=0.04) (41).

This data suggests that lower intratesticular retinoic acid is associated with impaired spermatogenesis; however, it is unclear from this cross-sectional data if the low retinoic acid is a result of the infertility or a cause of it. Only an interventional trial of retinoic acid in infertile men will answer the question of the ability of retinoic acid to improve spermatogenesis in this population.

Objectives

2.1 Primary Objective:

To determine the effect of 13-cis retinoic acid administration on total motile sperm count in men with oligoasthenoteratozoospermia

2.2 Secondary Objectives:

- o To determine the chance of pregnancy during treatment with 13-cis retinoic acid
- o To determine the concentration of 13-cis retinoic acid in the seminal plasma of treated men
- o To determine the side effects and tolerability of treatment with 13-cis retinoic acid

3. Rationale, Benefits and Risks

Male infertility is common and difficult to treat unless men have an easily identified gonadotropin deficiency. Many men have idiopathic infertility. Retinoids are necessary for spermatogenesis, but no controlled studies of retinoic acid administration to men with infertility have been conducted. We have shown that men with abnormal spermatogenesis have lower than normal levels of intratesticular retinoic acid, suggesting that intratesticular retinoic acid deficiency is associated with infertility. In this study, we aim to determine if retinoic acid therapy can improve sperm counts in men with low sperm counts. The medication, 13-cis retinoic acid is widely available and prescribed for the treatment of acne, suggesting that serious adverse events, especially at the low doses to be tested are unlikely.

4. Compliance

All aspects of this study will be performed according to GCP and ICH guidelines, under an active IND.

5. Study Design

We will conduct a prospective, three-arm, randomized, double-blinded, placebo-controlled interventional trial to determine the impact of therapy with 13-cis retinoic acid on sperm indices in infertile men. Sixty (n=20/group) infertile men with abnormal sperm analyses will be enrolled in a 24-week study of 20mg or 40 mg of 13-cis retinoic acid or matching placebo daily. The subjects will be closely followed for side effects related to treatment. The impact of treatment on indices of spermatogenesis will be determined by monthly seminal fluid analyses. All aspects of this study will be performed in compliance with Good Clinical Practice (GCP) regulations, ICH guidelines, the Declaration of Helsinki, and under an FDA Investigational New Drug (IND) application.

6. Duration of the Study

Subjects: Subjects will undergo a screening phase of up to 60 days. After fulfilling all entry criteria, the first 60 subjects will be randomly assigned to one of the three groups. The treatment phase will last for 24 weeks and subjects will have two post-treatment visits, about 4 and 12 weeks after the end of treatment.

Enrolment should be completed in approximately 12 months, resulting in total study duration of about 24 months including screening, treatment phase, end of study visit procedures, close out and data analysis.

7. Number of Subjects

60 men will participate in the study (n=20/arm)

8. Dosage and Administration

13-cis retinoic acid at 20 or 40 mg daily (purchased commercially) or matching placebo

9. Selection of Subjects

